6.3 Sequence and timing of drug administration

Vitamin D deficient patients will receive oral cholecalciferol 50,000 IU weekly starting at the time of diagnosis of vitamin D deficiency. Initiation of cholecalciferol therapy will not delay initiation of standard treatment for ovarian cancer, nor will it preclude enrollment in other clinical trials. Therapeutic dosing at 50,000 IU will continue weekly for a total of 8 weeks. Patients will then be given a prescription for maintenance dosing 2,000 IU cholecalciferol thereafter.

7.0 Dose Limiting Toxicities

IRB NUMBER: 7488
IRB APPROVAL DATE: 11/23/2021

As described above, vitamin D toxicity is extremely rare at the prescribed doses. In the unlikely event of evidence of vitamin D toxicity, treatment with vitamin D will be stopped. The Stephenson Cancer Center laboratory defines vitamin D toxicity as levels >100 ng/mL.

8.0 Study Parameters

8.1 Observations and Tests

The following observations and tests are to be performed and recorded on the appropriate form(s).

Observation and Tests	Screening	At each treatment visit	Completion of primary therapy	6 months after therapy completion	Time of recurrence or 1 year surveillance (if no recurrence)
History & Physical	1	X	X	X	X
Vital Signs and Weight	1				
Toxicity assessment	1	X	X	X	
Serum 25(OH)D	1		X	X	X
Serum Leptin	1		X	X	X

Serum Cr (and GFR)	1				
Red top and Purple topped blood tubes (for VDR SNP analysis)	1				
Serum pregnancy test (if potential exists)	1				

1. Must be obtained within 21 days prior to initiating protocol therapy.

All other blood draws (end of treatment, 6 months after therapy completion, Time of recurrence or 1 year surveillance) must occur within 8 weeks of expected date.

8.2 Translational Research

Requirements 8.2.1 Specimen

Requirements

A red topped and a purple topped tube of blood will be drawn from the patient at the time of screening.

The patient must give permission for her specimens to be used for this

IRB NUMBER: 7488
IRB APPROVAL DATE: 11/23/2021

mandatory translational research component. The participating institution is required to submit the patient's specimens as outlined below.

IRB NUMBER: 7488
IRB APPROVAL DATE: 11/23/2021

9.0 Evaluation Criteria

9.1.1 Response Criteria

9.1.1.1 Evaluation of Biomarkers

Clinical Response

If serum 25(OH)D is initially below the lower normal limit, it must normalize ($>20\text{ng/mL}$) for a patient to be considered experiencing a complete response to repletion.

9.1.2 Progression-Free Survival:

Progression-Free Survival (PFS) is defined as the duration of time from start of treatment to time of progression or death, whichever occurs first.

9.1.3 Survival:

Survival is defined as the duration of time from start of treatment to time of death or the date of last contact.

10.0 Duration of Study

10.1 Patients with serum 25(OH)D $<20\text{ng/mL}$ will receive cholecalciferol 50,000 IU weekly for 8 weeks.

10.2 Following repletion, patients will receive a prescription for 2,000 IU cholecalciferol as maintenance. Per Endocrine Society guidelines, patients should continue maintenance cholecalciferol indefinitely.

11.0 Study Monitoring and Safety Reporting Procedures

11.1 Adverse Event Reporting

IRB NUMBER: 7488
IRB APPROVAL DATE: 11/23/2021

11.1.1 Definitions (per 21 CFR 312.32(a)):

IRB NUMBER: 7488
IRB APPROVAL DATE: 11/23/2021

Adverse event: *“Any untoward medical occurrence associated with the use of a drug in humans, whether or not considered drug related.”* Life-threatening adverse event or life-threatening suspected adverse reaction: *“An adverse event or suspected adverse reaction is considered “lifethreatening” if, in the view of either the investigator or sponsor, its occurrence places the patient or subject at immediate risk of death. It does not include an adverse event or suspected adverse reaction that, had it occurred in a more severe form, might have caused death.”* Serious adverse event or serious suspected adverse reaction: *“An adverse event or suspected adverse reaction is considered “serious” if, in the view of the investigator, it results in any of the following outcomes:*

Death, a life-threatening adverse event, inpatient hospitalization or prolongation of existing hospitalization, a persistent or significant incapacity or substantial disruption of the ability to conduct normal life functions, or a congenital anomaly/birth defect. Important medical events that may not result in death, be life-threatening, or require hospitalization may be considered serious when, based upon appropriate medical judgment, they may jeopardize the patient or subject and may require medical or surgical intervention to prevent one of the outcomes listed in this definition. Examples of such medical events include allergic bronchospasm requiring intensive treatment in an emergency room or at home, blood dyscrasias or convulsions that do not result in inpatient hospitalization, or the development of drug dependency or drug abuse.”

Suspected adverse reaction: *“Suspected adverse reaction means any adverse event for which there is a reasonable possibility that the drug caused the adverse event. For the purposes of IND safety reporting, “reasonable possibility” means there is evidence to suggest a causal relationship between the drug and the adverse event. Suspected adverse reaction implies a lesser*

degree of certainty about causality than adverse reaction, which means any adverse event caused by a drug.”

Unexpected adverse event or unexpected suspected adverse reaction. “An adverse event or suspected adverse reaction is considered “unexpected” if it is not listed in the investigator brochure or is not listed at the specificity or severity that has been observed; or, if an investigator brochure is not required or available, is not consistent with the risk information described in the general investigational plan or elsewhere in the current application, as amended. For example, under this definition, hepatic necrosis would be unexpected (by virtue of greater severity) if the investigator brochure referred only to elevated hepatic enzymes or hepatitis. Similarly, cerebral thromboembolism and cerebral vasculitis would be unexpected (by virtue of greater specificity) if the investigator brochure listed only cerebral vascular accidents. “Unexpected,” as used in this definition, also refers to adverse events or suspected adverse reactions that are mentioned in the investigator brochure as occurring with a class of drugs or as anticipated from the pharmacological properties of the drug, but are not specifically mentioned as occurring with the particular drug under investigation.”

The descriptions and grading scales found in the revised NCI Common Terminology Criteria for Adverse Events (CTCAE) version 4.0 will be utilized for AE reporting. All appropriate treatment areas should have access to a copy of the CTCAE version 4.0. A copy of the CTCA version 4.0 can be downloaded from the CTEP web site (<http://ctep.cancer.gov>).

Furthermore, this study will fall under the purview of the Stephenson Cancer Center Data Safety Monitoring Committee (DSMC).

11.1.2 Reporting Expedited Adverse Events

IRB NUMBER: 7488
IRB APPROVAL DATE: 11/23/2021

In compliance with FDA regulations, as contained in 21 CFR 312.64, AEs must be reported to the Stephenson Cancer Center Data Safety Monitoring Committee by the investigator.

All serious and unexpected suspected adverse reactions must be reported directly to the Stephenson Cancer Center Data Safety Monitoring Committee either by telephone or by e-mail by the Investigator, study coordinator, clinical research associate, or other designated study personnel, within 24 hours of becoming aware of such an event. The Investigator also must report all such events promptly to the appropriate IRB/EC per their requirements.

11.1.3 Documenting Adverse Events

All AE information must be documented on the forms provided and approved by OU IRB. Additional follow-up information (e.g., test results, autopsy, and discharge summary) may be obtained to supplement AE reports. A copy of all initial and follow-up reports will be included with the patient's study files.

11.1.4 Causality Assessment of Adverse Events

The relationship between an AE and the study drug will be determined by the Investigator on the basis of his or her clinical judgment and the following definitions.

An AE will be considered associated with the use of study drug if there is a reasonable possibility that the AE may have been caused by the study drug. This definition applies to those AEs that are considered definitely, probably, and possibly related to the use of the study drug:

Definitely Related: An AE that follows a temporal sequence from administration of the study drug; follows a known response pattern to the study drug; improves after stopping the study drug (positive dechallenge) and reappears after repeat exposure (positive

IRB NUMBER: 7488
IRB APPROVAL DATE: 11/23/2021

rechallenge); and cannot be reasonably explained by known characteristics of the patient's clinical state or by other therapies

Probably Related: An AE that follows a reasonable temporal sequence from administration of the study drug; follows a known response pattern to the study drug; improves after dechallenge; and cannot be reasonably explained by the known characteristics of the patient's clinical state or by other therapies.

Possibly Related: An AE that follows a reasonable temporal sequence from administration of the study drug and follows a known response pattern to the study drug but could have been produced by the patient's clinical state or by other therapies. An AE may be considered not associated with the use of study drug if there is not a reasonable possibility that the AE may have been caused by the study drug. This definition applies to those AEs that are considered unlikely or not related to the use of the study drug:

Unlikely to be Related: An AE assessed as unlikely to be related to study drug is defined as an AE for which sufficient information exists to indicate a high improbability that the event is related to the study drug.

Not Related: An AE assessed as not related to study drug is defined as an AE for which sufficient information exists to indicate that the etiology is unrelated to the study drug. Two or more of the following variables apply:

- The AE does not follow a reasonable temporal sequence after administration of the study drug.
- The AE is readily explained by the patient's clinical state or other therapies.

IRB NUMBER: 7488
IRB APPROVAL DATE: 11/23/2021

- Negative dechallenge—the AE does not abate upon dose reduction or cessation of therapy (assuming that it is reasonable to expect abatement of the AE within the observed interval).

11.1.5 Severity Assessment of Adverse Events

Severity of AEs will be graded according to the CTCAE Version 4.0.

Adverse events not included in the CTCAE, Version 4.0 must be graded as follows: Mild, Moderate, Severe, Life-threatening, and Fatal according to the following definitions:

Mild: The AE is noticeable to the patient but does not interfere with routine activity.

Moderate: The AE interferes with routine activity but responds to symptomatic therapy or rest.

Severe: The AE significantly limits the patient's ability to perform routine activities despite symptomatic therapy.

Life-threatening: The AE places the patient at risk of death at the time of the event.

Fatal: The AE results in the death of the patient.

11.2 Study Monitoring

Safety oversight will be performed by Stephenson Cancer Center's (SCC) internal Data and Safety Monitoring Committee (DSMC). The DSMC is composed of individuals with the appropriate expertise in adult and pediatric hematology and medical oncology, radiation oncology, translational and correlative science, pharmacy, nursing and biostatistics. The DSMC operates under the rules of an approved data safety monitoring plan which complies with the National Cancer

IRB NUMBER: 7488
IRB APPROVAL DATE: 11/23/2021

Institute (NCI) guidelines published as *Essential Elements of a Data and Safety Monitoring Plan for Clinical Trials Funded by NCI* as of January 2005 and the “NIH Policy for Data and Safety Monitoring,” *NIH Guide for Grants and Contracts*, <http://grants.nih.gov/grants/guide/notice-files/not98-084.html>.

The Data Safety Monitoring Committee is charged with oversight of participant safety, study conduct and the validity and integrity of data for clinical trials at SCC. While the focus of the DSMC is to monitor interventional investigator initiated trials (IITs) that are not subject to external monitoring, it has the authority to monitor any SCC protocol when potential concerns are identified. The DSMC also has the authority to suspend or close a study until the principal investigator addresses any issues that may cause harm or increase risks to subjects. The DSMC reports all findings to the Institutional Review Board (IRB).

Under the direction of the DSMC chair, a full board meeting is convened on a biannual basis to review the accumulated safety data, accrual information, and additional information as stated in the DSMC plan.

DSMC Auditing

In addition to monitoring, the DSMC oversees an internal auditing process to ensure subject safety and data quality. All cancer-related clinical trials active at the SCC are eligible for audit; however, priority is placed on those clinical trials that are not monitored or audited by an outside entity. If an external entity conducts an audit of a clinical trial at the SCC, then the findings of that audit are reported to the DSMC, either through the formal audit report provided by the external auditing entity, if available, or from the PI, who will report any findings communicated during the audit process.

IRB NUMBER: 7488
IRB APPROVAL DATE: 11/23/2021

11.3 Data Disclosure and Patient Confidentiality

Patient medical information obtained as a result of this study is considered confidential. Disclosure to third parties other than those noted below is prohibited. All reports and communications relating to patients in this study will identify each patient only by their initials and number. Medical information resulting from a patient's participation in this study may be given to the patient's personal physician or to the appropriate medical personnel responsible for the patient's welfare. Data generated as a result of this study are to be available for inspection on request by Stephenson Cancer Center Data Safety Monitoring Committee, the clinical trial office auditors and monitors, the Investigational Review Board (IRB)/Ethics Committee (EC) and the Institutional Biosafety Review Committee (or equivalent). De-identified data generated by participation in this study will be securely shared with co-investigator ([name]) at the University of North Carolina at Chapel Hill for the purposes of data analysis and manuscript preparation.

All laboratory specimens, evaluation forms, reports, and other records that leave the site will be identified by a coded number to maintain patient confidentiality. All study records will be kept in a locked file cabinet or other secured area. All computer entry and networking programs will be identifiable only by coded numbers. Patient personal medical information may be reviewed by representatives of the Stephenson Cancer Center Data Safety Monitoring Committee, of the IRB, or of regulatory authorities in the course of monitoring the progress of the clinical trial. Every reasonable effort will be made to maintain such information as confidential.

12.0 Statistical Methods

Upon analysis, patients will be divided into two groups: Vitamin D Deficient Women and Vitamin D Normal Women.

IRB NUMBER: 7488
IRB APPROVAL DATE: 11/23/2021

Outcomes to be analyzed include differences in demographics, clinical, and tumor characteristics between groups, and differences in treatment-related morbidity or mortality between groups, including completion of treatment and treatment delays, and survival. Both 30-day postoperative surgical morbidity and chemotherapy-related morbidity will be assessed. The ability to normalize 25(OH)D levels with oral supplementation in the vitamin D deficient group will be evaluated.

Descriptive statistics will be used to summarize the demographic and clinical characteristics of patients. Chi-square and t-tests will be used to make comparisons between groups. Survival will be estimated with Kaplan-Meier curves and Cox proportional hazards regression. The anticipated enrollment is 100 patients based on estimated new diagnoses of ovarian cancer treated in the Division of Gynecologic Oncology annually at the Stephenson Cancer Center. Based on the previously mentioned unpublished data, we presume that at least 25 of the prospectively enrolled patients will be vitamin D deficient. All of the vitamin D deficient women will be repleted with oral vitamin D. We will compare outcomes between these patients and 75 vitamin D deficient ovarian cancer patients from previous years (these will include patients from the above-mentioned previous retrospective review as well as other patients with banked blood samples) using logistic regression. We will control for age, stage, and histology. With 25 prospective patients and 75 retrospective patients we will have 80% power to detect differences of 32% in chemotherapy delay between ovarian patients who were not vitamin D deficient (33%) and who were vitamin D deficient (65%).

Additionally, the association between serum leptin and 25(OH)D levels will be compared among groups, including any change in leptin levels observed in the vitamin D supplementation group. Because there is a positive linear association between BMI and serum leptin levels, BMI will be corrected for during analysis for potential relationships between serum leptin and 25(OH)D.

The proportion of patients with VDR *FokI* SNP will be assessed. We will also compare levels of vitamin D at diagnosis, differences in treatment-related morbidity or mortality including completion of treatment, treatment delays, survival and

IRB NUMBER: 7488
IRB APPROVAL DATE: 11/23/2021

response to vitamin D supplementation across 3 SNP allele groups (homozygous mutated, heterozygous mutated, homozygous wild type).

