1.2 Objective(s)

1.2.1 Primary objective:

1.2.1.1 To assess treatment-related morbidity (including 30-day postoperative surgical morbidity and chemotherapy-related morbidity) and 1-year disease-free survival in patients with deficient serum 25(OH)D levels at the time of ovarian, primary peritoneal, or fallopian tube cancer diagnosis who did and did not receive vitamin D repletion.

1.2.2 Secondary objectives:

1.2.2.1 To describe serum 25(OH)D levels, serum leptin levels, and VDR *FokI* SNP status among newly diagnosed ovarian, primary peritoneal, or fallopian tube cancer patients.

1.2.2.2 To determine the proportion of patients with ovarian, primary peritoneal, or fallopian tube cancer that have deficient vitamin D at diagnosis and have normal serum 25(OH)D after oral vitamin D supplementation during primary therapy.

1.2.2.3 To identify potential relationships between serum 25(OH)D and serum leptin levels when controlling for BMI.

1.2.2.4 To evaluate change of serum leptin levels with repletion of 25(OH)D in patients with low levels at the time of ovarian primary peritoneal, or fallopian tube cancer diagnosis.

1.3 Translational Research Objectives:

1.3.1 To evaluate VDR *FokI* SNP status relationship with serum 25(OH)D levels and treatment-related morbidity and cancer outcomes.

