2.2 Vitamin D Deficiency in Cancer

Vitamin D has been well-studied due to its role in many important cellular pathways. Laboratory and observational studies suggest that it plays a role in many diseases such as autoimmune diseases, cardiovascular disease, diabetes, cancer risk and cancer survival. The correlation of low serum 25(OH)D with elevated risk for malignancy has been best studied in colorectal cancer [4]. Decreased levels of serum 25(OH)D have been correlated with increased risk of breast cancer in postmenopausal women. [5]. Women receiving chemotherapy and anti-hormonal therapy for breast cancer experience treatment-induced bone loss due to premature ovarian failure or direct cytotoxic effects of chemotherapy. This causes an increase in the osteoporosis and skeletal morbidity risk [6]. Similar effects can be estimated in ovarian cancer patients given that standard treatment requires surgical menopause as well as cytotoxic therapy in the majority of patients.

The majority of studies pertaining to vitamin D and ovarian cancer concern the association of low serum 25(OH)D with increased cancer risk. Limited study has been performed investigating the correlation of serum vitamin D and ovarian cancer prognosis or treatment-related morbidity. A study performed in Australia investigated serum 25(OH)D levels at the time of diagnosis of ovarian cancer in 670 women. They noted a significant association between higher circulating 25(OH)D concentrations and longer survival in women with ovarian cancer when adjusting for other clinical predictors of

survival [7]. Similarly, Walentowicz-Sadlecka et al. reported low serum 25(OH)D concentrations in women with ovarian cancer undergoing primary cytoreductive surgery to be associated with lower overall survival[8]. The impact of repletion of vitamin D in ovarian, primary peritoneal, or fallopian tube cancer patients has yet to be determined.

Findings from an unpublished study performed at the University of Oklahoma have shown an inverse correlation between low levels of serum vitamin D and treatment-related morbidity in women aged 65 years and older with ovarian cancer. More specifically, when comparing median serum 25(OH)D levels between patients who experienced chemotherapy delay ≥ 7 days versus those who did not, lower mean 25(OH)D levels were significantly associated with chemotherapy delays (23.6 ng/dL, n=28 no delay versus 14.6 ng/dL, n=30 delay, p=.0112). (Figure 1)[9].

[figure not shown]

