2.3 Leptin and Ovarian Cancer

Leptin is an adipokine that appears to stimulate growth of cancer cells while decreasing apoptosis [10]. Serum leptin levels have also been linked to elevated levels of pro-inflammatory cytokines in malignancy [11]. Retrospective analysis of data from NHANES III revealed an inverse relationship between serum leptin levels and cancer death in women [12]. In ovarian cancer, there is some data to show that lower leptin levels may be associated with increased initial tumor burden and subsequent increases in leptin may correlate with complete cytoreduction [13]. Further study is needed to better understand the role of leptin in ovarian cancer. Vitamin D receptors are involved in production of adipokines such as leptin; however, the response of serum leptin levels to repletion of vitamin D remains unclear [1]. Conflicting data exists between meta-analyses investigating changes in leptin following correction of vitamin D levels in humans [1]. This study aims to assess for potential relationships between serum 25(OH)D levels and leptin levels, including any changes that may occur during repletion of 25(OH)D.

Women with treatment-related morbidity often experience delays in treatment, changes in chemotherapeutic regimens and surgical or chemotherapy-related complications requiring hospitalization. Identifying modifiable risk factors among patients with ovarian cancer (including fallopian tube and primary peritoneal cancer) that can prevent treatment-related morbidity represents an important goal in the care of these women.

Safety:

Cholecalciferol is a generally safe and well-tolerated medication. Repletion of vitamin D is considered standard of care and will be undertaken utilizing current available guidelines [14].

Translational Research Background:

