#### 5. Summary of Study Population

##### a. Patient Disposition

1. Demographic, clinical, and disease characteristics and outcomes will be collected from all patients prospectively. Descriptive statistics will be used to summarize the demographic and clinical characteristics of patients. Chi-square and t-tests will be used to make comparisons between groups.
2. The association between serum leptin and 25(OH)D levels will be compared among groups, including any change in leptin levels observed in the vitamin D supplementation group. Because there is a positive linear association between BMI and serum leptin levels, BMI will be corrected for during analysis for -potential relationships between serum leptin and 25(OH)D.

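### The leptin-25(OH)D analysis corrects for BMI only; tumor burden is a possible confounder if it also relates to 25(OH)D, and stage should be added to the model

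*Protocol*

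**What the plan says.** Secondary objective 1.2.2.3 in the protocol is "To identify potential relationships between serum 25(OH)D and serum leptin levels when controlling for BMI". The method in protocol section 12.0 is one sentence: "BMI will be corrected for during analysis for potential relationships between serum leptin and 25(OH)D". SAP section 5a, item 2, gives the same reason and the same single covariate: "Because there is a positive linear association between BMI and serum leptin levels, BMI will be corrected for during analysis". Neither document specifies a regression model or names a further covariate for this analysis.

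Two other places bear on the choice:

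- Protocol section 2.3 reports some data that "lower leptin levels may be associated with increased initial tumor burden".
- Protocol section 12.0, on the logistic regression comparing repleted women with historical deficient women, states "We will control for age, stage, and histology". SAP section 2b repeats this. In both documents it belongs to the outcome comparison and is not carried over to the leptin analysis.

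**The concern.** The plan's reason for correcting for BMI is that BMI is associated with leptin. By its own background section, tumor burden may also be associated with leptin, but the leptin analysis makes no allowance for it. The plan does treat stage as something to control for elsewhere.

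If women with more extensive disease also tend to have lower 25(OH)D, both markers would fall together with advancing disease. A regression of one on the other, adjusted for BMI alone, would then show a positive association even if vitamin D and leptin had nothing to do with each other. A chance of false discovery well above the nominal 5% would attach to the only analysis that addresses objective 1.2.2.3. The primary comparison is not affected.

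**Working it through.** The documents give no figure for this analysis, so there is none to reproduce. The check has two parts: which links the documents supply, and what follows if the missing one is assumed.

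**Links needed for confounding**

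| Link | In the documents? |
|---|---|
| Tumor burden and leptin | Yes, hedged and without an effect size (protocol 2.3) |
| Tumor burden and 25(OH)D | No. The nearest text is protocol 2.2, on survival: a "significant association between higher circulating 25(OH)D concentrations and longer survival in women with ovarian cancer when adjusting for other clinical predictors of" survival |

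Confounding needs both rows.

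**Inputs**

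- n = 100, the anticipated prospective enrollment (protocol 12.0), taken as complete data.
- Assumed: 70% advanced stage, so the variance of the stage indicator is v = 0.7 × 0.3 = 0.21.
- Assumed: stage is independent of BMI, and BMI has slopes of 0.6 on leptin and −0.3 on 25(OH)D.
- Assumed: residual SD of 1 for both markers and no direct leptin-25(OH)D link.
- Advanced stage lowers leptin by s_L and 25(OH)D by s_D, in residual SD. These are varied.

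**Formula**

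The partial correlation given BMI that stage alone produces is

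r = s_L·s_D·v / √[(1 + s_L²v)(1 + s_D²v)].

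By Fisher's z with one covariate, the test statistic is centered at m = √(100 − 1 − 3) × atanh(r) = 9.80 × atanh(r). The two-sided 5% rejection rate is Φ(m − 1.96) + Φ(−m − 1.96).

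**Example, both shifts 0.8**

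- r = 0.64 × 0.21 / (1 + 0.64 × 0.21) = 0.1344 / 1.1344 = 0.118.
- m = 9.80 × 0.119 = 1.17.
- Rate = Φ(−0.79) + Φ(−3.13) = 21.5%.

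**Results, BMI-only model**

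| s_L | s_D | r | Formula | Simulation |
|---|---|---|---|---|
| 0.8 | 0 | 0 | 5.0% | about 5% |
| 0.3 | 0.3 | 0.019 | 5.4% | 5% to 6% |
| 0.8 | 0.3 | 0.047 | 7.5% | 7% to 7.5% |
| 0.5 | 0.5 | 0.050 | 7.8% | 7% to 9% |
| 0.8 | 0.5 | 0.077 | 11.7% | 11% to 11.5% |
| 0.8 | 0.8 | 0.118 | 21.5% | 21% |
| 1.0 | 1.0 | 0.174 | 40.5% | 40% to 42% |

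The simulations used 4,000 to 8,000 data sets per run from the same model. With stage added, the rejection rate was between 4.4% and 5.5% throughout. That is the best case, because stage itself is the simulated cause. If stage is only a proxy for burden, part of the bias remains.

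**If only the documented link exists**

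There is no bias, but adding stage still gains precision. With s_L = 0.8 and s_D = 0, the standard error of the 25(OH)D slope is about √1.1344 / √97 = 0.108 with BMI only, and 1 / √96 = 0.102 with stage added.

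**The case against.** The strongest objection is that a confounder must relate to both markers, and the documents supply one relation only. This stands. A reader might infer from the survival findings in protocol 2.2 that low 25(OH)D marks advanced disease, and so treat tumor burden as an established common cause. The text does not support that. In the 670-woman study the association held after adjustment for other clinical predictors of survival, which is not evidence that 25(OH)D tracks stage. The second study is described only in terms of overall survival. With the leptin link alone the false-positive rate stays at 5%, and if the 25(OH)D shift is weak (0.3 SD against 0.8 SD for leptin) it rises only to about 7%. The high rates need large shifts in both markers, for which the documents give no evidence.

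It can also be said that the objective is secondary, seeks only potential relationships at fixed BMI, and is delivered as written. That is fair, and it limits the weight of the point. The plan also compares tumor characteristics between the vitamin D groups, so a stage imbalance would be seen. It would not, however, be carried into the leptin model.

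What survives is narrower. The plan names one leptin correlate and leaves out another that its own background mentions, when a covariate that stands in for it is already used elsewhere in the same section.

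**Conclusion.** The point holds as a possible confounder, conditional on a link between tumor burden and 25(OH)D that neither document states. If that link is absent, the BMI-only analysis is unbiased and only slightly less precise. If it is present, the false-positive rate is about 7% to 9% with both shifts at 0.5 residual SD, and 21% to 41% at 0.8 to 1.0 SD. These rates rest on n = 100, 70% advanced disease and effect sizes chosen for illustration.

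A reader might also infer that a spurious association would count as support for hypothesis 1.1.2. The documents do not support that reading. The hypothesis concerns leptin change with repletion and is addressed by objective 1.2.2.4, whereas this check concerns the association under objective 1.2.2.3, modeled at a single time point. The remark in protocol 2.3 that "subsequent increases in leptin may correlate with complete cytoreduction" bears on the change analysis. That is a separate question, and nothing calculated here tests it.

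**What to change.** In protocol section 12.0 and SAP section 5a, item 2:

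- Specify a regression for leptin and 25(OH)D that includes BMI and stage.
- Report the BMI-only model beside it, so that objective 1.2.2.3 is still answered as worded and the effect of adding stage is visible.
- State in advance that no leptin-25(OH)D relationship will be claimed if it disappears when stage is added.
- Describe the result as an association, because stage is only a proxy for tumor burden.
- Do not present this analysis as a test of hypothesis 1.1.2.

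The cost is a change of wording and one to a few degrees of freedom, depending on how stage is coded, in a secondary, exploratory analysis. Stage is already needed for the outcome model, so no new data collection is required.
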